2.2.3 Research object

The subjects included in this study were children with neuroblastoma disease. The study will be

conducted in the medical institutions of Nantong University Affiliated Hospital, lasting for 2 years. It is expected that 20 cases will participate in this study.

2.2.4 Research objectives

- i) Identifying tumor differentiation related specific transcripts through Third Generation Sequencing Technology of cell lines;
- ii) Identify possible differential expression through Deep Sequencing Technology of clinical tissue samples.

3、Specific research methods (including inclusion criteria, sample size calculation, study grouping, intervention and control, specific research process, primary and secondary research indicators, and statistical analysis)

3.1.Inclusion and exclusion criteria

3.1.1 Inclusion criteria

- ① Children with neuroblastoma range in age from 0 to 14, regardless of gender;
- ② Preoperative imaging examinations indicate patient with neuroblastoma;
- ③ Before postoperative chemotherapy, the patient's physical strength is good. At the same time, the results of white blood cells, neutrophils, hemoglobin, platelets, and other test indicators are all within normal range, which is in line with the treatment conditions of the relevant chemotherapy and immunotherapy;
- ④ Preoperative pathological examination of the patient reveals neuroblastoma;
- ⑤ Patients have no other history of malignant tumors;
- ⑥ Patients voluntarily participate and sign informed consent and can comply with the study visit plan and other protocol requirements.

3.1.2 Exclusion Criteria:

- ① Patients who are found to have distant metastasis or ascites on preoperative examination are excluded;
- ② Individuals with severe liver and kidney dysfunction, as well as those with autoimmune diseases are excluded;
- ③ Patients with severe cardiovascular disease who can not tolerate general anesthesia are excluded;
- ④ Patients who have other malignancies or blood disorders are excluded.

3.1.3Exit and Termination Criteria

- ① If serious adverse events occur, the experiment should be terminated in a timely manner;

[figure not shown]
- ② External information (such as other high-quality research or evidence) proves that the intervention plan is ineffective or effective, and there is no need to continue the current clinical trial;
- ③ According to the planned mid-term analysis, the expected therapeutic differences were achieved, and it has been observed that the intervention plan of the experimental group is significantly better than that of the control group.

3.2. Sample size calculation and research grouping

Recruitment is mainly conducted in children with neuroblastoma within the past 2 years, excluding cases that are not suitable for enrollment. This study expects recruitment of 20 children with neuroblastoma.

3.3. Research specific processes

3.3.1 technology roadmap

3.3.2 Specific sequencing

7 types of neuroblastoma cell lines: SK-N-SH、SH-SY5Y、SH-EP、IMR-32、NB-19、SK-N-BE、SK-K-AS; Detection of gene transcriptional isomer expression using third-generation

sequencing, divided into NMYC amplification group: IMR-32, NB-19, SK-N-BE and NMYC non amplification group: SK-N-SH, SH-SY5Y, SH-EP, SK-N-AS, and compare the two; SH-SY5Y, SH-EP are differentiated from SK-N-SH, and comparison of three cell lines reveals differentiation related specific transcripts.

i) Sequencing experiment process

The process of full-length transcriptome sequencing experiment includes three steps:

- a.Sample extraction and testing;
- b.Library construction;
- c.On machine sequencing.

Kangsheng Zhenyuan strictly controls every production step of sample testing, database construction, and sequencing to ensure the output of high-quality data.

ii) Sample extraction and testing

After extracting total RNA from tissue samples, we use the following methods for detection.

Only after the detection results meet the requirements can we proceed with library construction:

- a.Nanodrop detection of RNA purity (OD 260/280), concentration, and whether the nucleic acid absorption peak is normal; A single database construction requires a total RNA content of 1 μ g, a concentration of $\geq 200\text{ng}/\mu\text{L}$, and an OD260/280 between 1.8 and 2.2.
- b.Agilent 2100 accurately detects the integrity of RNA, with detection indicators including: RIN value, 28S/18S, baseline elevation, and 5S peak;
- c.Electrophoretic detection of RNA sample bands for dispersion, presence of impurities, or contamination of genomic DNA.

iii) Library construction

After passing the sample testing, the library is constructed, and the main process is as follows:

a.Synthesize full-length cDNA of mRNA using Clonetech SMARTerTM PCR cDNA Synthesis Kit. The 3' end of eukaryotic mRNA has a polyA tail structure. Primers with Oligo dT are used to pair with poly-A as A-T base pairs for reverse synthesis of cDNA, and primers are added at the end of the full-length cDNA synthesized by reverse synthesis. Amplify the full-length cDNA obtained through PCR, purify the product with magnetic beads, and quantify using Qubit 3.0.

b.Purify and amplify the full-length cDNA using magnetic beads, and remove some small fragments of cDNA below 1kb.

c.Perform end repair on full-length cDNA and connect to SMRT dumbbell-shaped connectors.

d.Digest the unconnected fragments using exonuclease and purify them again using magnetic beads to obtain a sequencing library.

e.After the construction of the library is completed, the quality of the library is tested, and only

after the test results meet the requirements can machine sequencing be carried out.

The detection method is:

- a. Use Qubit 3.0 for accurate quantification;
- b. Use Agilent 2100 to detect the library size, and only after the library size meets expectations can machine sequencing be performed.

iv) On-machine sequencing

After passing the library inspection, use PacBio sequencer to perform full-length transcriptome sequencing according to the target offline data volume.

3.4 Main and secondary research indicators and statistical analysis

Main and secondary indicators: comparison between genes :IMR-32, NB-19, SK-N-BE and NMYC non-amplified groups:SK-N-SH, SH-SY5Y, SH-EP, and SK-N-AS; SH-SY5Y and SH-EP are derived from SK-N-SH differentiation, and differentiation related specific transcripts can be found by comparing the three cell lines.

Statistical analysis: ① Sample size estimation and grouping method, collecting clinical data of laparoscopic/open neuroblastoma surgery performed at Nantong University Affiliated Hospital from 2024 to 2026. ② Grouping method: Random grouping ③ Research data collection and statistical analysis. Researchers should ensure the accuracy, completeness, and timeliness of the data in the Case Report Form (CRF) and all required reports provided to them. Statistical analysis used survival analysis and repeated measurement methods to analyze the data of the experimental group and control group. t-test was used for quantitative data, chi square test was used for count data, Kaplan Meier method and Cox regression analysis were used for survival analysis, and Stata 26.0 was used for statistical software. P<0.05 was considered statistically significant.

4、Ethic principles

Meet the requirements of the Ethics Committee of Nantong University Affiliated Hospital.

5、Plan and Progress

2024.04.01–2024.08.31 Long segment sequencing of 7 neuroblastomas, collecting neuroblastoma and adjacent control groups;

2024.09.01–2025.11.31 Analyze sequencing data and discover over 100 new splicing fragments; Defective cell lines with successful 2–3 gene new splicing.

2025.12.01–2026.03.31 Organize and analyze data, and write a paper.

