2.2 Research content and design

2.2.1 research contents

- i) Collect 20 clinical neuroblastoma tumor specimens;
- ii) Deep analysis of sequencing data and tumor specific transcripts;

2.2.2 experimental design

- i) 7 types of neuroblastoma cell lines: SK-N-SH、SH-SY5Y、SH-EP、IMR-32、NB-19、SK-N-BE、SK-K-AS; Detection of gene transcriptional isomer expression using Third Generation Sequencing Technology, divided into NMYC amplification group: IMR-32, NB-19, SK-N-BE and NMYC non amplification group: SK-N-SH, SH-SY5Y, SH-EP, SK-N-AS, and compare the two; SH-SY5Y, SH-EP are differentiated from SK-N-SH, and comparison of three cell lines reveals differentiation related specific transcripts.

- ii) Deep sequencing of tissues from 20 clinical neuroblastoma specimens;

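### The NMYC contrast pools two lines described as differentiated into the non-amplified group without adjustment, so differentiation shifts can bias NMYC fold changes and mask true NMYC transcripts

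*Combined protocol and SAP*

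**What the plan says.** Section 2.2.2 sets up the comparison as "divided into NMYC amplification group: IMR-32, NB-19, SK-N-BE and NMYC non amplification group: SK-N-SH, SH-SY5Y, SH-EP, SK-N-AS, and compare the two", and section 3.3.2 repeats it. Section 3.4 lists it first under a joint label: "Main and secondary indicators: comparison between genes :IMR-32, NB-19, SK-N-BE and NMYC non-amplified groups:SK-N-SH, SH-SY5Y, SH-EP, and SK-N-AS". It does not say which indicator is main and which is secondary.

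The same sections say that two of the four non-amplified lines come from a third by differentiation. Section 2.2.2 has "SH-SY5Y, SH-EP are differentiated from SK-N-SH, and comparison of three cell lines reveals differentiation related specific transcripts", and section 3.4 has "SH-SY5Y and SH-EP are derived from SK-N-SH differentiation, and differentiation related specific transcripts can be found by comparing the three cell lines". The first objective in 2.2.4 is "Identifying tumor differentiation related specific transcripts through Third Generation Sequencing Technology of cell lines".

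No differentiation status is given for IMR-32, NB-19, SK-N-BE or SK-N-AS. Nothing says that the NMYC contrast is adjusted for differentiation, restricted to some of the lines, or read against the three-line comparison. The only relevant method named is general: "t-test was used for quantitative data, chi square test was used for count data". It appears alongside the experimental and control groups and is not expressly assigned to the cell lines.

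**The concern.** The plan looks for transcripts that differ between SK-N-SH and its two derived lines, so it expects such differences. It then averages those derived lines into one side of the NMYC comparison. A transcript that responds to differentiation alone will show a non-zero NMYC difference. A transcript that responds to both NMYC and differentiation can have its NMYC difference reduced, cancelled or exaggerated.

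Such overlap is plausible on the plan's own account, because section 1.1.1(i) describes MYCN as a regulator of differentiation. It matters for follow-up: section 5 foresees defective cell lines for only 2–3 genes, and any gene chosen from the NMYC list could be wrongly attributed or overlooked.

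This is a bias in the group difference. It is separate from the fact that three of the four non-amplified lines are related. Averaging those three into one lineage deals with the relatedness, but still leaves (2/3)d/2 = d/3 of a common shift d in the contrast.

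**Working it through.** The plan gives no effect size, power or sample-size figure for the cell-line comparison, so there is no stated figure to reproduce.

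**Inputs from the plan.** Three amplified and four non-amplified lines; two of the four described as differentiated (2.2.2, 3.3.2, 3.4); significance at P<0.05 (3.4).

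**Assumptions.** Normal log expression with between-line SD 1, additive effects, independent lines, a two-sided pooled t-test. M is the NMYC effect; d1 and d2 are the shifts in SH-SY5Y and SH-EP, all in SD units. Unless stated otherwise, the amplified lines and SK-N-AS are undifferentiated.

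**Bias.** Mean of the amplified lines = M. Mean of the non-amplified lines = (0 + d1 + d2 + 0)/4. Expected contrast = M − (d1+d2)/4.

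- Equal shifts d: M − 0.5d.
- Opposite shifts (d1 = −d2): M, no bias.
- If k of the 3 amplified lines are also differentiated, with a common shift, the coefficient of d is k/3 − 2/4: −0.50, −0.17, +0.17 or +0.50 for k = 0, 1, 2, 3.

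**Standard errors.** Planned 3 v 4: √(1/3+1/4) = 0.76, with 5 df. Restricted 3 v 2 (SK-N-SH and SK-N-AS only): √(1/3+1/2) = 0.91, with 3 df. Ratio 0.913/0.764 = 1.20.

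**Simulation, 200,000 transcripts per setting.**

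| M | d1, d2 | Planned 3 v 4: estimate | Planned: P<0.05 | Restricted 3 v 2: P<0.05 | Single derived-line term: P<0.05 |
|---|---|---|---|---|---|
| 3 | 0, 0 | 3.0 | 88% | 60% | 69% |
| 3 | 1, 1 | 2.5 | 68% | 60% | 69% |
| 3 | 2, 2 | 2.0 | 31% | 60% | 69% |
| 3 | 3, 3 | 1.5 | 6% | 60% | 70% |
| 3 | −3, −3 | 4.5 | 88% | 60% | 69% |
| 3 | 3, 0 | 2.25 | 28% | 60% | 36% |
| 3 | 3, −3 | 3.0 | 16% | 60% | 3% |
| 0 | 1, 1 | −0.5 | 6.3% | 5% | 5% |
| 0 | 2, 2 | −1.0 | 7.4% | 5% | 5% |
| 0 | 3, 3 | −1.5 | 6.2% | 5% | 5% |
| 0 | 4, 4 | −2.0 | 4.1% | 5% | 5% |

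The restricted estimate equals M in every row, because the derived lines are not in it. False-positive calls in the planned test stay low because the shift also inflates the within-group variance. As a common d grows, the pooled t tends to 0.5/√[(4×0.25/5)(1/3+1/4)] = 1.46, below the 5-df critical value of 2.57. The same inflation explains why opposite shifts leave the estimate unbiased but still cut power to 16%.

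**The case against.** The confounding rests partly on silence. The plan mentions differentiation only to explain the SK-N-SH family comparison, and says nothing about the amplified lines. This stands: the size and sign of the bias depend on an unstated fact. It also limits the remedy, since k differentiated amplified lines would put k/3 of a common shift into the restricted contrast. A common shift in both derived lines is likewise assumed. A reader might infer that the NMYC contrast always carries half of any differentiation effect; the documents do not support that, because the weight is (d1+d2)/4 and can be zero.

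A reader might also infer that the pooling will produce many falsely significant NMYC transcripts. Under a t-test at 0.05 it does not: the highest rate found is about 7%.

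The t-test is not expressly assigned to the cell lines, so the rejection rates are conditional on that choice. The bias in the group difference is not; it arises in any comparison of the two group means. Nor does the plan make this its main contrast: 3.4 does not separate main from secondary, and the cell-line objective in 2.2.4 names only differentiation transcripts.

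Finally, this is exploratory work, and the planned three-line comparison will already show many of the affected transcripts. That is a fair reason not to replace the planned contrast. It does not remove the problem, because no rule connects the two lists.

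**Conclusion.** The point holds in a limited form. The plan pools two lines that it describes as differentiated into the non-amplified group, expects their transcripts to differ from the parent's, and makes no allowance for this in the NMYC contrast. With undifferentiated amplified lines the difference is shifted by (d1+d2)/4.

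The main harm is biased fold changes and lost true NMYC transcripts: at M = 3 and a common d = 3, an estimate of 1.5 and significance in 6%, against 88% with no shift. With no NMYC effect and d = 3 the estimate is 1.5 SD in size instead of 0, which would distort a list ranked by fold change even though few such transcripts reach P<0.05.

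These figures rest on SD 1, additive effects, independent lines, a pooled t-test and assumed values of M and d. They illustrate size and are not predictions. A stronger conclusion, that the planned contrast is invalid and should be discarded, does not follow: when there is no differentiation shift it is the more powerful analysis. This is a cheap improvement to make before the data are analysed.

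**What to change.** In 3.4:

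- Keep the planned 3 v 4 contrast.
- Report beside it the contrast of IMR-32, NB-19 and SK-N-BE against SK-N-SH and SK-N-AS only.
- Label any NMYC transcript that also differs between SK-N-SH and its derived lines as not separable from differentiation, unless the NMYC difference holds in the restricted contrast. Say in advance what counts as holding.
- State the differentiation status of all seven lines, since the reading of both contrasts depends on it.

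Do not rely on one model with a single derived-line term. It assumes equal shifts in SH-SY5Y and SH-EP; with shifts of 3 and 0 it reaches significance in 36%, and with +3 and −3 in 3%, against 60% for the restricted contrast.

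The cost is a few sentences and one extra comparison on data already planned. The restricted contrast has 3 df instead of 5, a standard error about 20% larger (0.91 v 0.76 SD), and 60% rather than 88% significance for a 3 SD effect when there is no shift. Some true NMYC transcripts will therefore carry the caveat.

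### Comparing SK-N-SH with its two derived lines cannot by itself show that a transcript is differentiation related, because differentiation state is confounded with cell line

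*Combined protocol and SAP*

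**What the plan says.** Three sections carry the inference.

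- Section 2.2.2 states the premise, "SH-SY5Y, SH-EP are differentiated from SK-N-SH", and concludes that comparing the three lines reveals the transcripts.
- Section 3.3.2 repeats it: "comparison of three cell lines reveals differentiation related specific transcripts".
- Section 3.4, under the main and secondary indicators, says "SH-SY5Y and SH-EP are derived from SK-N-SH differentiation" and then that "differentiation related specific transcripts can be found by comparing the three cell lines".

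Objective i in section 2.2.4 is worded more broadly: "Identifying tumor differentiation related specific transcripts through Third Generation Sequencing Technology of cell lines". It does not name the three lines, but the three-line comparison is the only step in the readable text that appears to serve it.

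The readable text gives no number of cultures or libraries per line, no induced-differentiation condition, no time course, no second parent-and-derived family, no differentiation marker and no rule for assigning the label. The timeline in section 5 mentions "Long segment sequencing of 7 neuroblastomas". That is consistent with one library per line but does not establish it.

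**The concern.** The label is attached by the comparison alone. A transcript that differs among SK-N-SH, SH-SY5Y and SH-EP becomes, in the plan's terms, related to differentiation. Two separately maintained derived lines can differ from their parent, and from each other, for reasons unrelated to differentiation, such as clonal selection or drift in culture. Shared origin reduces differences in genetic background but does not remove these.

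At stake is the conclusion attached to one of the listed indicators and, apparently, to objective i. Followed as written, the study would report line-to-line differences as differentiation biology. The sequencing data would still be useful, but the stated meaning would not follow from them.

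**Working it through.** **No plan figure to reproduce.** The documents give no effect size, SD, replicate number or sample-size calculation for this comparison. The check is therefore whether the effect can be identified at all, followed by an illustration under stated assumptions.

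**Step 1: identifiability.** Inputs, from sections 2.2.2, 3.3.2 and 3.4: one parent line and two derived lines. For one transcript, write culture k of line l as

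y(l,k) = mu + state(l) + line(l) + e(l,k).

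The expected difference between a derived line D and the parent P is

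E[mean(D) − mean(P)] = {state(D) − state(P)} + {line(D) − line(P)}.

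Only the sum of the two brackets can be estimated. The number of cultures r does not appear, so raising r makes the sum more precise without splitting it.

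With the line as the unit:
- If each line is its own state, residual df = 3 − 3 = 0.
- If the two derived lines are pooled against the parent, df = 3 − 2 = 1, and the smallest exact permutation P is 1/C(3,1) = 1/3. Pooling assumes that the derived lines share one state, which the plan does not say, so this second figure is illustrative.

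**Step 2: illustration of size.** These inputs are assumptions, not from the documents: r = 3 cultures per line; no differentiation effect; between-line SD equal to t times the within-line SD; normal errors; one-way F test across the three lines at P<0.05.

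- df = 2 and 3(r − 1) = 6.
- With numerator df 2 and denominator df m, P(F > x) = (1 + 2x/m)^(−m/2). For m = 6 this is (1 + x/3)^(−3). Setting it to 0.05 gives a critical value of 5.143.
- Line differences multiply the F ratio by 1 + r·t², so the flag rate is P(F > 5.143/(1 + 3t²)).

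| t | 1 + 3t² | 5.143/(1 + 3t²) | Flag rate |
|---|---|---|---|
| 0 | 1 | 5.143 | 5.0% |
| 0.5 | 1.75 | 2.939 | 12.9% |
| 1 | 4 | 1.286 | 34.3% |
| 2 | 13 | 0.396 | 69.0% |

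A simulation of 20,000 transcripts per setting gave 5.0%, 12.9%, 34.3% and 69.1%, in agreement.

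**Step 3: more cultures do not help.** Take r = 10 and t = 1. Then m = 27, the critical value is 3.354, and 3.354/(1 + 10) = 0.305. The flag rate is (1 + 2 × 0.305/27)^(−13.5) = 74%, against 34% with 3 cultures. These are real line differences detected more often; only the differentiation label is unsupported.

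**Step 4: is the comparison confirmed elsewhere?**
- Section 5 plans defective cell lines for 2–3 genes. It does not say that the genes come from this comparison and names no differentiation readout for them.
- Section 2.2.4 ii aims the 20 clinical specimens at differential expression and does not link them to differentiation.
- Section 3.3.1, the technology roadmap, has no readable content in the text available.

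**The case against.** The strongest reply is that this is exploratory discovery work, that a related transcript is only an associated one, and that no treatment decision depends on the label. This stands in part: it supports keeping the comparison and limits how serious the point is. It does not rescue the wording, because the sections say the comparison reveals or finds such transcripts, not that it nominates candidates.

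Several stronger readings are tempting, and the documents do not support them.

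- *The plan has no confirmation at all.* This cannot be said. The roadmap in 3.3.1 is unreadable here, so a validation step shown only there cannot be excluded. Such a step would not remove the confounding in the comparison itself.
- *Objective i defines the label by the three-line contrast.* It does not; it refers only to sequencing of cell lines.
- *The plan will apply P<0.05 to these data.* Section 3.4 directs its survival and repeated-measures methods to "analyze the data of the experimental group and control group" and does not tie its t-test or P<0.05 threshold to the three lines. The percentages above are therefore not error rates of a planned test.
- *Most candidates will go without follow-up, since 2–3 genes compare with a target to "discover over 100 new splicing fragments".* That target is not specific to this comparison, and the length of the three-line candidate list is unknown.
- *A same-direction shift in both derived lines would be the telling pattern.* That presumes they share one state, and no section assigns any of the three lines to a state.
- *The planned defective lines would settle the matter.* They might not. If each is a single derived line set against its parent, the same clone confounding could return.

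**Conclusion.** The concern holds as a limit on what may be concluded. One parent and two derived lines confound differentiation state completely with line or clone, at any number of cultures, so the comparison alone cannot justify the label that sections 2.2.2, 3.3.2 and 3.4 give its output. This result needs no assumption about variances or tests.

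The size is illustrative only: about 13%, 34% or 69% of transcripts flagged with no differentiation effect, under the assumed 3 cultures per line and SD ratios of 0.5, 1 and 2. The true ratio and the number of cultures are not in the documents.

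The absence of a confirming readout is established for the readable text only. The point does not invalidate the sequencing data or its use for generating candidates.

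**What to change.** 1. In 2.2.2, 3.3.2 and 3.4, restate the output as descriptive nomination, without P-values, of *candidate transcripts differing among SK-N-SH, SH-SY5Y and SH-EP*. Align 2.2.4 i so that the objective matches.
2. Select candidates by a read-support and difference rule fixed before the data are seen, with values left to the sponsor.
3. State in 3.4 that line and differentiation effects cannot be separated in this comparison.
4. Do not conclude from this comparison alone that a transcript is differentiation related. If independent confirmation is already planned, for example in the roadmap, state it in 3.4, name its readout and reserve the label for confirmed transcripts.

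The cost is rewording four places and writing one selection rule; no new samples or lines are needed. The downside is a more modest claim from the cell-line data. Adding a differentiation assay that is not already planned would be new laboratory work, and this change does not depend on it.

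### Section 3.4 names no method suited to isoform expression for its main 3 v 4 cell-line comparison; a variance-moderated model with FDR control and lineage handling would serve better at almost no cost

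*Combined protocol and SAP*

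**What the plan says.** The main indicator in section 3.4 is a transcript comparison between two sets of cell lines: "comparison between genes :IMR-32, NB-19, SK-N-BE and NMYC non-amplified groups:SK-N-SH, SH-SY5Y, SH-EP, and SK-N-AS". Sections 2.2.2 and 3.3.2 give the same split, 3 amplified lines against 4 non-amplified. Section 3.4 adds that "SH-SY5Y and SH-EP are derived from SK-N-SH differentiation", so three of the four non-amplified lines share one origin.

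For tests, section 3.4 offers "t-test was used for quantitative data" and "chi square test was used for count data", with Kaplan-Meier and Cox methods for survival and the rule "P<0.05 was considered statistically significant". It names no normalisation, no isoform-level model, no sharing of variance information across isoforms and no multiplicity rule, and it states no replicate libraries per line. The tests are introduced by a sentence about two trial arms, "Statistical analysis used survival analysis and repeated measurement methods to analyze the data of the experimental group and control group", which follows text on clinical surgery data. They are never tied to the cell-line comparison.

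**The concern.** Full-length transcriptome sequencing yields expression values for thousands of isoforms from seven lines. A t-test on each isoform separately has almost no information about that isoform's variance. Isoforms whose variance happens to come out small rise to the top of the list, and genuine differences with an unluckily large variance estimate drop out. A model that pools variance information across isoforms uses the same data better.

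A chi-square test on read counts would be worse in kind: it treats each read as an independent observation and ignores variation between lines, which is the variation that matters for a statement about amplified against non-amplified disease.

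The plan's timetable takes only 2–3 genes forward to modified cell lines. The quality of the ranked list therefore decides what gets followed up.

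**Working it through.** **No figure to reproduce.** The documents state no power, effect size, SD or number of isoforms for this comparison. Everything below beyond the line counts and the 0.05 level is an assumption.

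**Degrees of freedom.** Seven lines: 3 + 4 − 2 = 5. Counting SK-N-SH, SH-SY5Y and SH-EP once leaves two non-amplified lineages: 3 + 2 − 2 = 3.

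**Ordinary t-test, equal variances, 3 v 4.** With d the difference in SDs, the noncentrality is d × √(3×4/7) = 1.309d on 5 df. The two-sided 0.05 critical value is 2.571. Power is 19% at d = 1, 56% at d = 2 and 88% at d = 3; it reaches 50% at d = 1.85 and 80% at d = 2.68.

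**Moderated test.** The variance used is (d₀s₀² + νs²)/(d₀ + ν), referred to ν + d₀ df, where d₀ and s₀² are estimated from all isoforms and ν is the residual df. Idealised with ν = 5 and d₀ = 4, this gives 9 df, and the 80% point moves only from 2.68 to 2.41 SD. At a strict level the heavy tail of t on 5 df costs far more: at 0.001 the critical values are 6.87 (5 df) and 4.78 (9 df), and power at d = 4 is 30% against 66%.

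**Simulation.** 15,000 isoforms, 5% truly different (750), isoform variances drawn with prior df 6, typical SD 0.5 on the log2 scale, normal data, independent lines, 20 data sets per case. A 4-fold difference is 2/0.5 = 4 SD; 2.8-fold is 1.5/0.5 = 3 SD; 2-fold is 1/0.5 = 2 SD. Repeat runs agreed to within about three percentage points.

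| Case | Threshold | t-test | moderated |
|---|---|---|---|
| 4 SD, 3 v 4 | P<0.05 | 92% | 97% |
| 4 SD, 3 v 2 | P<0.05 | 73% | 94% |
| 4 SD, 3 v 4 | FDR 5% | 23% | 79% |
| 4 SD, 3 v 2 | FDR 5% | 0% | 35% |
| 3 SD, 3 v 4 | FDR 5% | 0.6% | 27% |
| 3 SD, 3 v 2 | FDR 5% | 0% | 0% |
| 2 SD, 3 v 4 | FDR 5% | 0% | 0% |

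At 4 SD, 3 v 4, FDR 5%, that is about 750 × 0.23 ≈ 170 true isoforms found against 750 × 0.79 ≈ 590.

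**The plan's own threshold.** With 15,000 − 750 = 14,250 null isoforms, 14,250 × 0.05 ≈ 713 pass by chance. In the first row the t-test list has 750 × 0.92 = 690 true entries, so 713/(690 + 713) ≈ 51% of it is false. For the moderated test it is 713/(728 + 713) ≈ 49%. Moderation alone does not make unadjusted 0.05 usable.

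**Ranking, no threshold.** For 3 v 2, the share of the top 100 isoforms that are truly different is 73.5% (t-test) against 95.9% (moderated) at 4-fold, and 59.5% against 84.8% at 2.8-fold.

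**Sensitivity.** With 10,000 isoforms, 10% different, 3 v 4, FDR 5% and d₀ from 2.5 to 30, power goes from at most 0.1% to 0–15% at 2 SD, from 3–10% to 22–79% at 3 SD, and from 37–49% to 62–98% at 4 SD. With sparser signal (30,000 isoforms, 5% different, d₀ = 4) the 3 SD case stays poor, 0.9% to 3.5%, while 4 SD goes from 23% to 67%.

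**Shared origin.** With an assumed correlation of 0.5 among the three related lines, analysed as 3 v 4 at a nominal 5% FDR and 4 SD, realised FDR is about 14% for the t-test and about 19% for the moderated test. At correlations of 0.3 and 0.8 the figures are 8% v 11% and 28% v 32%.

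**The case against.** **The t-test may not be meant for isoforms.** The sentence introducing the tests concerns two trial arms, follows clinical text, and sits beside a chi-square clause under which read counts could equally fall. This stands: a reader might infer that the plan chose the t-test for isoforms, and the text does not show that. But if the t-test is for clinical variables only, the main indicator has no suitable stated analysis, and if chi-square is meant, the unit is wrong. Each reading calls for the same edit.

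**The loss is not general.** A reader might infer that the t-test loses most true differences and that moderation recovers them. The documents do not support this. Their only threshold is unadjusted 0.05, where with equal variances the t-test on 3 v 4 loses more than half only below about 1.9 SD, and where moderation adds 5 points in the 4 SD case. The large gap needs FDR control, which the plan does not contain, and large differences. This stands and limits the claim. Against it, unadjusted 0.05 lets through about 713 null isoforms under the assumed numbers, so some error-rate control is needed anyway.

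**The simulation favours the moderated test.** Variances come from the distribution that test assumes, with normal data and no low counts. This also stands; the figures are indicative.

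**Moderation is not a complete repair.** On 3 v 4 with correlated lines it exceeds the nominal FDR slightly more than the t-test does. The fix must therefore handle lineage too.

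**Conclusion.** The point holds as an unsuitable specification. For its main comparison section 3.4 offers only an ordinary t-test or a chi-square test, and neither suits isoform expression. If the t-test is what is applied, a variance-moderated model gives a modest gain at the plan's 0.05 level, larger once common origin reduces the contrast to 3 v 2, and it ranks candidates better there. Under FDR control the gain is large from roughly 3 to 4 SD upwards, depending on the assumed number of isoforms, share truly different and spread of variances. At about 2 SD or less it is little or nothing.

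The sizes rest on assumed SDs, effects and isoform numbers. The line counts, df and absence of an isoform-level method come from the documents. The change is worth making but does not by itself rescue the comparison: it does not supply replicates or remove the dependence among the three related lines.

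**What to change.** In section 3.4, state separately how isoform expression will be analysed:

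- normalise for library size, then fit either an empirical-Bayes moderated linear model to log counts or a negative-binomial model with shrunken dispersion;
- control the FDR across all isoforms tested, at a stated level, in place of unadjusted 0.05;
- treat SK-N-SH, SH-SY5Y and SH-EP as one lineage, by averaging them or by modelling a within-lineage correlation. Fixed lineage effects will not do, because lineages are nested within the amplification groups;
- reserve the t-test and chi-square test for clinical variables.

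The cost is SAP wording and standard free software, with no extra samples or sequencing. The added assumption is that isoform variances share a common distribution, which can be checked in the data. Counting the related lines once lowers apparent power (79% to 35% in the 4 SD case at FDR 5%), but the higher figure assumes seven independent lines, which the plan's own description of their origin contradicts.
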